5.4.2 Reporting Requirements for Serious Adverse Events and Adverse Events of Special Interest

5.4.2.1 Events That Occur prior to Study Drug Initiation

After informed consent has been obtained but prior to initiation of study drug, only serious adverse events caused by a protocol-mandated intervention should be reported. The paper Clinical Trial Serious Adverse Event/Adverse Event of Special Interest Reporting Form provided to investigators should be completed and submitted to the Sponsor or its designee immediately (i.e., no more than 24 hours after learning of the event), either by faxing or by scanning and emailing the form using the fax number or email address provided to investigators.

5.4.2.2 Events That Occur after Study Drug Initiation

After initiation of study drug, serious adverse events and adverse events of special interest will be reported until 28 days after the final dose of study drug. Investigators should record all case details that can be gathered immediately (i.e., within 24 hours after learning of the event) on the Adverse Event eCRF and submit the report via the electronic data capture (EDC) system. A report will be generated and sent to Roche Safety Risk Management by the EDC system.

In the event that the EDC system is unavailable, the paper Clinical Trial Serious Adverse Event/Adverse Event of Special Interest Reporting Form provided to investigators should be completed and submitted to the Sponsor or its designee immediately (i.e., no more than 24 hours after learning of the event), either by faxing or by scanning and emailing the form using the fax number or email address provided to investigators. Once the EDC system is available, all information will need to be entered and submitted via the EDC system.

Instructions for reporting serious adverse events that occur 28 days after the last dose of study treatment are provided in Section 5.6.

5.4.3 Reporting Requirements for Pregnancies

5.4.3.1 Pregnancies in Female Patients

Female patients of childbearing potential will be instructed to immediately inform the investigator if they become pregnant during the study or within 6 months after the final dose of any study drug. A paper Clinical Trial Pregnancy Reporting Form should be completed and submitted to the Sponsor or its designee immediately (i.e., no more than

24 hours after learning of the pregnancy), either by faxing or by scanning and emailing the form using the fax number or email address provided to investigators. Pregnancy should not be recorded on the Adverse Event eCRF. The investigator should discontinue study treatment and counsel the patient, discussing the risks of the pregnancy and the possible effects on the fetus. Monitoring of the patient should continue until conclusion of the pregnancy. Any serious adverse events associated with the pregnancy (e.g., an event in the fetus, an event in the mother during or after the pregnancy, or a congenital anomaly/birth defect in the child) should be reported on the Adverse Event eCRF. In addition, the investigator will submit a Clinical Trial Pregnancy Reporting Form when updated information on the course and outcome of the pregnancy becomes available.

5.4.3.2 Pregnancies in Female Partners of Male Patients

Male patients will be instructed through the Informed Consent Form to immediately inform the investigator if their partner becomes pregnant during the study or within 6 months after the final dose of any study treatment. A paper Clinical Trial Pregnancy Reporting Form should be completed and submitted to the Sponsor or its designee immediately (i.e., no more than 24 hours after learning of the pregnancy), either by faxing or by scanning and emailing the form using the fax number or email address provided to investigators. Attempts should be made to collect and report details of the course and outcome of any pregnancy in the partner of a male patient exposed to study treatment. The pregnant partner will need to sign an Authorization for Use and Disclosure of Pregnancy Health Information to allow for follow-up on her pregnancy. After the authorization has been signed, the investigator will submit a Clinical Trial Pregnancy Reporting Form when updated information on the course and outcome of the pregnancy becomes available. An investigator who is contacted by the male patient or his pregnant partner may provide information on the risks of the pregnancy and the possible effects on the fetus, to support an informed decision in cooperation with the treating physician and/or obstetrician.

5.4.3.3 Abortions

Any abortion should be classified as a serious adverse event (as the Sponsor considers abortions to be medically significant), recorded on the Adverse Event eCRF, and reported to the Sponsor immediately (i.e., no more than 24 hours after learning of the event; see Section [5.4.2](#)).

5.4.3.4 Congenital Anomalies/Birth Defects

Any congenital anomaly/birth defect in a child born to a female patient exposed to study treatment or the female partner of a male patient exposed to study treatment should be classified as a serious adverse event, recorded on the Adverse Event eCRF, and reported to the Sponsor immediately (i.e., no more than 24 hours after learning of the event; see Section [5.4.2](#)).

5.4.4 Reporting Requirements for Cases of Overdose, Medication Error, Drug Abuse, or Drug Misuse

Overdose (accidental or intentional), medication error, drug abuse, and drug misuse (hereafter collectively referred to as "special situations"), are defined as follows:

- Accidental overdose: accidental administration of a drug in a quantity that is higher than the assigned dose
- Intentional overdose: intentional administration of a drug in a quantity that is higher than the assigned dose
- Medication error: accidental deviation in the administration of a drug
 - In some cases, a medication error may be intercepted prior to administration of the drug.
- Drug abuse: intentional excessive use of a drug that may lead to addiction or dependence, physical harm, and/or psychological harm
- Drug misuse: intentional deviation in the administration of a drug that does not qualify as drug abuse

In cases where drug is to be self-administered by the patient, drug misuse could involve the drug being administered to someone other than the patient.

Special situations are not in themselves adverse events, but may result in adverse events. Each adverse event associated with a special situation should be recorded separately on the Adverse Event eCRF. If the associated adverse event fulfills seriousness criteria, the event should be reported to the Sponsor immediately (i.e., no more than 24 hours after learning of the event; see Section 5.4.2). For idasanutlin, adverse events associated with special situations should be recorded as described below for each situation:

- Accidental overdose: Enter the adverse event term. Check the "Accidental overdose" and "Medication error" boxes.
- Intentional overdose: Enter the adverse event term. Check the "Intentional overdose" box. If drug abuse is suspected, check the "Drug abuse" box. If drug abuse is not suspected, check the "Drug misuse" box.
- Medication error that does not qualify as an overdose: Enter the adverse event term. Check the "Medication error" box.
- Medication error that qualifies as an overdose: Enter the adverse event term. Check the "Accidental overdose" and "Medication error" boxes.
- Drug abuse that does not qualify as an overdose: Enter the adverse event term. Check the "Drug abuse" box.
- Drug abuse that qualifies as an overdose: Enter the adverse event term. Check the "Intentional overdose" and "Drug abuse" boxes.
- Drug misuse that does not qualify as an overdose: Enter the adverse event term. Check the "Drug misuse" box.

- Drug misuse that qualifies as an overdose: Enter the adverse event term. Check the "Intentional overdose" and "Drug misuse" boxes.

In addition, all special situations associated with idasanutlin, regardless of whether they result in an adverse event, should be recorded on the Adverse Event eCRF and reported to the Sponsor immediately (i.e., no more than 24 hours after learning of the event).

Special situations should be recorded as described below:

- Accidental overdose: Enter the drug name and "accidental overdose" as the event term. Check the "Accidental overdose" and "Medication error" boxes.
- Intentional overdose: Enter the drug name and "intentional overdose" as the event term. Check the "Intentional overdose" box. If drug abuse is suspected, check the "Drug abuse" box. If drug abuse is not suspected, check the "Drug misuse" box.
- Medication error that does not qualify as an overdose: Enter the name of the drug administered and a description of the error (e.g., wrong dose administered, wrong dosing schedule, incorrect route of administration, wrong drug, expired drug administered) as the event term. Check the "Medication error" box.
- Medication error that qualifies as an overdose: Enter the drug name and "accidental overdose" as the event term. Check the "Accidental overdose" and "Medication error" boxes. Enter a description of the error in the additional case details.
- Intercepted medication error: Enter the drug name and "intercepted medication error" as the event term. Check the "Medication error" box. Enter a description of the error in the additional case details.
- Drug abuse that does not qualify as an overdose: Enter the drug name and "drug abuse" as the event term. Check the "Drug abuse" box.
- Drug abuse that qualifies as an overdose: Enter the drug name and "intentional overdose" as the event term. Check the "Intentional overdose" and "Drug abuse" boxes.
- Drug misuse that does not qualify as an overdose: Enter the drug name and "drug misuse" as the event term. Check the "Drug misuse" box.
- Drug misuse that qualifies as an overdose: Enter the drug name and "intentional overdose" as the event term. Check the "Intentional overdose" and "Drug misuse" boxes.
- Drug administered to someone other than the patient: Enter the drug name and "patient supplied drug to third party" as the event term. Check the "Drug misuse" box.

As an example, an accidental overdose that resulted in a headache would require the completion of two Adverse Event eCRF pages, one to report the accidental overdose and one to report the headache. The "Accidental overdose" and "Medication error" boxes would need to be checked on both eCRF pages.

5.5 FOLLOW-UP OF PATIENTS AFTER ADVERSE EVENTS

5.5.1 Investigator Follow-Up

The investigator should follow each adverse event until the event has resolved to baseline grade or better, the event is assessed as stable by the investigator, the patient is lost to follow-up, or the patient withdraws consent. Every effort should be made to follow all serious adverse events considered to be related to study drug or trial-related procedures until a final outcome can be reported. Patients with ongoing hematologic adverse events should be monitored with weekly blood counts until resolution. The final outcome must be reported in the eCRF. Hematologic adverse events are not reportable for patients for whom myelosuppression arises as a result of confirmed relapsed disease.

During the study period, resolution of adverse events (with dates) should be documented on the Adverse Event eCRF and in the patient's medical record to facilitate source data verification.

All pregnancies reported during the study should be followed until pregnancy outcome.

5.5.2 Sponsor Follow-Up

For serious adverse events, adverse events of special interest, and pregnancies, the Sponsor or a designee may follow up by telephone, fax, email, and/or a monitoring visit to obtain additional case details and outcome information (e.g., from hospital discharge summaries, consultant reports, autopsy reports) in order to perform an independent medical assessment of the reported case.

5.6 ADVERSE EVENTS THAT OCCUR AFTER THE ADVERSE EVENT REPORTING PERIOD

After the end of the adverse event reporting period (defined as 28 days after the final dose of study drug), all deaths, regardless of cause, should be reported through use of the Long-Term Survival Follow-Up eCRF.

In addition, if the investigator becomes aware of a serious adverse event that is believed to be related to prior exposure to study drug, the event should be reported through use of the Adverse Event eCRF. However, if the EDC system is not available, the investigator should report these events directly to the Sponsor or its designee, either by faxing or by scanning and emailing the paper Clinical Trial Serious Adverse Event/Adverse Event of Special Interest Reporting Form using the fax number or email address provided to investigators.

5.7 EXPEDITED REPORTING TO HEALTH AUTHORITIES, INVESTIGATORS, INSTITUTIONAL REVIEW BOARDS, AND ETHICS COMMITTEES

The Sponsor will promptly evaluate all serious adverse events and adverse events of special interest against cumulative product experience to identify and expeditiously

communicate possible new safety findings to investigators, IRBs, ECs, and applicable health authorities based on applicable legislation.

To determine reporting requirements for single adverse event cases, the Sponsor will assess the expectedness of these events using the following reference documents:

- Idasanutlin Investigator's Brochure
- Local prescribing information for cytarabine
- Local prescribing information for daunorubicin

The Sponsor will compare the severity of each event and the cumulative event frequency reported for the study with the severity and frequency reported in the applicable reference document.

Reporting requirements will also be based on the investigator's assessment of causality and seriousness, with allowance for upgrading by the Sponsor as needed.

A sample size of 20 favorable/intermediate-risk patients (including patients in the dose-escalation phase already on RP2D) is deemed sufficient for the point estimate and for the lower end of the 90% CI to rule out a clinically uninteresting probability of CR <65% if the observed proportion is >85%. Of note, a CR proportion of 65%-80% (Fernandez et al. 2009; Löwenberg et al. 2009; Burnett et al. 2015; Luskin et al. 2016) is expected for favorable/intermediate-risk patients under current 7+3 standard of care (see Table 15).

Table 15 Potential 90% CI for the True Probability of Achieving Complete Response at End of Induction/Consolidation for N=20 in Favorable/Intermediate-Risk Patients

| Observed Proportion of Patients Achieving Complete Response at End of Induction/Consolidation | Two-Sided 90% Clopper-Pearson CI for True Population Proportion (%) |
|---|---|
| 70 | (49, 86) |
| 75 | (54, 90) |
| 80 | (60, 93) |
| 85 ^a | (66, 96) |
| 90 | (72, 98) |

^a 17 patients with complete response out of 20 patients in total (85%).

In addition, the post-consolidation cohort will enroll 30 idasanutlin-naive patients in remission and MRD-positive at the end of induction.

6.2 SUMMARIES OF PATIENTS CHARACTERISTICS

Major protocol violations and discontinuations from the study will be listed.

Demographics as well as the incidence of treatment discontinuation for reasons other than disease progression will be tabulated. Data related to administration of study treatment components will be listed, and any dose modifications will be flagged. The

number of doses, treatment cycles, and the average dose received for each cohort will be summarized using descriptive statistics (mean, standard deviation, median, and range). Number of patients who enroll, discontinue, or complete the study will be summarized.

6.3 EFFICACY ANALYSES

Efficacy analyses will be performed including all patients who received at least one dose of any study drug given in combination or as a single agent.

Data from patients enrolled during the dose-escalation phase will be analyzed separately, by dose. Data from patients who were treated at the RP2D during the dose-escalation phase will be pooled with the corresponding cohort of the expansion phase (favorable/intermediate cohort). Data from the favorable/intermediate cohort, high-risk cohort (expansion phase), and post-consolidation cohort will be analyzed separately, without direct comparison among cohorts. Response definitions used in the section below are provided in [Appendix 19](#).

6.3.1 Primary Efficacy Endpoint

The primary efficacy analysis will be the estimation of the proportion of patients with a CR at the end of induction treatment.

Point estimates will be presented, along with the corresponding two-sided 90% Clopper-Pearson exact CIs. Patients without a post-baseline tumor assessment will be considered non-responders.

6.3.2 Secondary Efficacy Endpoints

The following secondary efficacy endpoints will be analyzed in patients enrolled during specified phases through use of the same methods described for the primary efficacy endpoint:

Dose-escalation or expansion phase

- Proportion of patients with a CR, CRi, or CRp at the end of induction treatment
- Proportion of patients with a CR or CRh at the end of induction treatment
- Proportion of patients with a negative MRD status at the end of induction treatment

Post-consolidation phase

- Proportion of patients converting from MRD-positive to MRD-negative status at any time during treatment

The following secondary efficacy endpoints will be analyzed in patients enrolled during the dose-escalation and expansion phases:

- EFS, defined as the time from initiation of study treatment (for post-consolidation patients, date of initiation of induction treatment prior to this study) to treatment

failure (failure to achieve CR, CRi, CRp, or CRh), hematologic relapse, or death from any cause, whichever occurs first

Patients with no EFS event at the time of analysis will be censored at the date of last response assessment. Patients with no EFS event and no postbaseline response assessment will be censored at Day 1.

- OS, defined as the time from initiation of study treatment to death from any cause
Patients who have not died at the time of analysis will be censored at the date the patient was last known to be alive.
- RFS in patients who achieve remission (CR, CRi, CRp, or CRh), defined as the time from remission to the date of hematologic relapse or death from any cause, whichever occurs first
Patients with no RFS event at the time of analysis will be censored at the date of last response assessment.

The following secondary efficacy endpoints will be analyzed in patients enrolled during the post-consolidation phase:

- EFS, defined as the time from initiation of induction treatment (prior to study entry) to hematologic relapse or death from any cause, whichever occurs first
Patients with no EFS event at the time of analysis will be censored at the date of last response assessment. Patients with no EFS event and no postbaseline response assessment will be censored at Day 1.
- OS, defined as the time from remission (prior to study entry) to death from any cause
Patients who have not died at the time of analysis will be censored at the date the patient was last known to be alive.
- RFS in patients who achieved remission (CR, CRi, CRp, or CRh), defined as the time from remission (prior to study entry) to the date of hematologic relapse or death from any cause, whichever occurs first
Patients with no RFS event at the time of analysis will be censored at the date of last response assessment.

The following secondary efficacy endpoint will be analyzed in patients enrolled during all phases:

- Change from baseline in patient-reported disease-related symptoms and health-related quality of life at specified timepoints, as assessed through use of the FACIT-Fatigue, EORTC QLQ-C30 (selected scales), and EORTC Item Library (selected symptoms)

EFS, OS, and RFS will be analyzed descriptively using the Kaplan–Meier method (Kaplan and Meier 1958).

Where medians are reached, the corresponding estimated median will be provided, along with the 95% CI by means of the Brookmeyer and Crowley method (Brookmeyer and Crowley 1982). In addition, when available at the time of the analysis, landmark estimates of the proportion of patients who are event free at 6 months, 9 months, 1 year, and 2 years will be provided, along with 95% asymptotic CIs using Greenwood's formula for standard errors.

Descriptive summary statistics and change from baseline will be calculated at each assessment timepoint for the FACIT-Fatigue, EORTC QLQ-C30 scales, and EORTC Item Library symptoms. Further details of the PRO analyses will be provided in the Statistical Analysis Plan.

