2.2.2 Secondary Efficacy Objectives

The secondary objective for this study is to evaluate the efficacy of idasanutlin when given in combination with cytarabine and daunorubicin as induction treatment, in combination with cytarabine as consolidation treatment, and/or as a single agent during maintenance treatment, on the basis of the following endpoints, which will be analyzed in patients enrolled during specified phases:

Dose-escalation or expansion phase

- Proportion of patients with a CR, complete remission with incomplete blood count recovery (CRi), or complete remission with incomplete platelet count recovery (CRp) at the end of induction treatment
- Proportion of patients with a CR or complete remission with partial hematologic recovery (CRh) at the end of induction treatment
- Proportion of patients with a negative MRD status at the end of induction treatment
- EFS, defined as the time from initiation of study treatment to treatment failure (failure to achieve CR, CRi, CRp, or CRh), hematologic relapse, or death from any cause, whichever occurs first
- OS, defined as the time from initiation of study treatment to death from any cause
- RFS in patients who achieve remission (CR, CRi, CRp, or CRh), defined as the time from remission to the date of hematologic relapse or death from any cause, whichever occurs first

Post-consolidation phase

- Proportion of patients converting from MRD-positive to MRD-negative status at any time
- EFS, defined as the time from initiation of induction treatment (prior to study entry) to hematologic relapse or death from any cause, whichever occurs first
- OS, defined as the time from remission (prior to study entry) to death from any cause
- RFS in patients who achieved remission (CR, CRi, CRp, or CRh), defined as the time from remission (prior to study entry) to the date of hematologic relapse or death from any cause, whichever occurs first

All phases

- Change from baseline in patient-reported disease-related symptoms and health-related quality of life at specified timepoints, as assessed through use of the Functional Assessment of Chronic Illness Therapy (FACIT)-Fatigue, European Organisation for Research and Treatment of Cancer Quality-of-Life Questionnaire, Core 30 (EORTC QLQ-C30) (selected scales), and European Organisation for Research and Treatment of Cancer (EORTC) Item Library (selected symptoms)

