3.1.3 Post-Consolidation Phase and Expansion Phase

The post-consolidation cohort of 30 patients is designed to further assess the safety and efficacy of idasanutlin given as a single agent to idasanutlin treatment-naïve patients in a maintenance setting. Patients will start maintenance right after consolidation completion.

The expansion phase is designed to further assess the safety and efficacy of idasanutlin in combination with cytarabine and daunorubicin at its RP2D in induction and in combination with cytarabine in consolidation followed by a single-agent maintenance.

The expansion phase (approximately 40 patients) is composed of two cohorts: 20 patients with favorable or intermediate risk and 20 patients with high risk (see [Table 3](#)).

All expansion patients will be enrolled and treated as described in [Table 4](#), and patients in the post-consolidation cohort will receive maintenance treatment as described in [Table 5](#).

In the expansion cohorts, patients who achieve remission after up to 2 induction cycles will receive chemotherapy consolidation treatment up to 4 cycles with 1.5 mg/m² cytarabine or allo-HSCT (as per site guidelines). Patients who achieved a confirmed remission at the end of chemotherapy consolidation or allo-HSCT or who underwent allo-HSCT in MLFS after induction will receive maintenance treatment for 12 cycles (see [Table 4](#)).

Patients receiving chemotherapy consolidation in the expansion should start maintenance right after consolidation completion. Patients receiving allo-HSCT consolidation should start within 90 days of the transplant and a full pre-transplant hematologic response assessment must be provided if the transplant is performed more than 4 weeks after end of induction.

On the basis of safety, tolerability, and clinical benefit and after consultation with the Medical Monitor, patients may be allowed to continue maintenance past 12 cycles.

Table 3 Post-Consolidation and Expansion Cohorts

| Cohorts | Population |
|---|---|
| Post-consolidation | Idasanutlin treatment-naïve patients in remission who received chemotherapy consolidation but were MRD positive after induction as locally assessed |
| Expansion: favorable or intermediate risk | Favorable and intermediate risk patients (ELN 2017; see Appendix 8) |
| Expansion: high risk | Adverse-risk patients (ELN 2017; see Appendix 8) and secondary AML defined as AML evolving from AHD |

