4.1.1.3 Inclusion Criteria for Patients in the Post-Consolidation Phase

Patients in the post-consolidation cohort must meet the following inclusion criterion for enrollment in the study:

- Documented/confirmed AML according to WHO (Arber et al. 2016) in remission after induction, within 21 days of end of last chemotherapy consolidation cycle, and were MRD positive at the end of induction as per local laboratory assessment (validated quantitative AML-specific MRD assessment with a >0.1% threshold)

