4.5.7 Laboratory Assessments

Normal ranges for the study laboratory parameters must be submitted to the Sponsor before the study starts.

Samples for the following laboratory tests will be sent to the study site's laboratory for analysis.

- Hematology: WBC count, RBC count, hemoglobin, hematocrit, platelet count, differential count (neutrophils, eosinophils, basophils, monocytes, lymphocytes, blasts, promyelocytes, myelocytes, metamyelocytes)
 - A manual differential (including WBC) may be needed if an automated differential does not provide blasts. Each differential should add up to 100% (or as close as possible).
- Biochemistry: procalcitonin, glucose, urea or BUN, serum creatinine, creatinine clearance (at screening only determined by Cockcroft-Gault Formula), AST, ALT, LDH, ALP, total bilirubin (and direct bilirubin where total bilirubin > ULN), total protein, albumin, calcium, phosphorus, magnesium, sodium, potassium, bicarbonate, chloride, and uric acid)
- Urinalysis using standard dipstick assessment (pH, protein, glucose, blood, ketones, and leukocytes)
 - This must be supplemented with laboratory quantification of any potentially relevant abnormalities as deemed necessary by the investigator.
- *C. difficile* infection at screening
- Viral serology
 - Hepatitis B testing includes hepatitis B surface antigen and total hepatitis B core antibody.
 - Hepatitis C testing includes hepatitis C virus antibody.
- Coagulation: INR, aPTT (or PTT), and PT
- Serum pregnancy test in females of child bearing potential and postmenopausal females with less than 1 year of amenorrhea
- Bone marrow aspirate pathology report

Total cells counted, absolute mature neutrophils, mature eosinophils, mature basophils, monocytes, lymphocytes, blasts, promyelocytes, myelocytes, metamyelocytes, plasma cells, pronormoblasts, normoblasts, and nucleated erythrocytes

Quantitative and validated AML-specific MRD assessment at end of induction in the post-consolidation cohort

- Bone marrow biopsy (leukemia histology, cellularity, percent cellularity, percent blasts)

4.5.8 Mandatory Samples for Pharmacokinetic, Pharmacodynamic Biomarker, and Exploratory Biomarker Analyses

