Appendix 1: Schedule of Activities (cont.)

Table 4: Maintenance in Post-Consolidation Cohort (cont.)

| Assessment/Procedure | Screening ^a | Maintenance (28-Day Cycle; ± 2 day) All Cycles | | | | | | |
|---|------------------------|---|----|----|----|----|----------------|----------------|
| | Days – 14 to – 1 | D1 | D2 | D3 | D4 | D5 | D15 | D28 (Q3M) |
| Hematology ^k | x | x | | | | | x ^l | |
| HMRA | | | | | | | | x |
| Bone marrow sampling for HMRA ^m | x | | | | | | | x |
| Bone marrow sampling for MRD/Flow, EDTA, PAXgene ^{® n} | x | | | | | | | x |
| Whole blood sampling for flow, for EDTA and clinical | x | x | | | | | | x ^o |
| RBR sampling, blood serum and plasma (optional) | x | | | | | | | |
| PK sampling | | Refer to Appendix 2 | | | | | | |
| Concomitant medications | x | To be recorded continually; see Section 4.4 | | | | | | |
| Adverse events | | To be assessed continually; see Section 5.3.1 | | | | | | |
| Idasanutlin treatment (PO QD) ^p | | x | x | x | x | x | | |

AML=acute myeloid leukemia; CT=computed tomography; CTCAE=Common Terminology Criteria for Adverse Events; D=day; ECHO=echocardiogram; ECOG=Eastern Cooperative Oncology Group; eCRF=electronic Case Report Form; EDTA=ethylenediaminetetraacetic acid; EORTC=European Organisation for Research and Treatment of Cancer; EORTC QLQ-C30=EORTC Quality-of-Life Questionnaire–Core 30; EQ-5D-5L=EuroQol 5-Dimension, 5-Level; FACIT=Functional Assessment of Chronic Illness Therapy; HMRA=hematologic malignancy response assessment; MRD=minimal residual disease; MUGA= multiple-gated acquisition (scan); PK=pharmacokinetic; PO=orally; PRO=patient-reported outcome; PRO-CTCAE=Patient-Reported Outcomes Common Terminology Criteria for Adverse Events; Q3M=every 3 months; QD=once a day; RBR=Research Biosample Repository; TB=tuberculosis.

^a The screening period starts with the signing of the Informed Consent Form, including the optional Informed Consent Form if appropriate. Results of standard-of-care tests or examinations performed prior to obtaining informed consent and within the defined window may be used as screening and baseline assessments; such tests do not need to be repeated for screening purposes.

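### The post-consolidation MRD-conversion endpoint names no reference sample and counts all dosed patients, so patients already MRD-negative at entry can be scored either way

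*Combined protocol and SAP*

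**What the plan says.** **Entry.** Section 4.1.1.3 admits patients in remission who "were MRD positive at the end of induction as per local laboratory assessment", within 21 days of the end of the last consolidation cycle. Table 3 in Section 3.1.3 describes them as patients "who received chemotherapy consolidation but were MRD positive after induction as locally assessed", and Section 6.1 states that "the post-consolidation cohort will enroll 30 idasanutlin-naive patients in remission and MRD-positive at the end of induction". No criterion asks for MRD positivity after consolidation or at screening.

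**MRD samples.** The plan holds two results from before the first dose:
- Section 4.5.7 lists "Quantitative and validated AML-specific MRD assessment at end of induction in the post-consolidation cohort". This is the local result used for enrolment, and Section 4.1.1.3 gives it a threshold above 0.1%.
- Appendix 1, Table 4 marks "Bone marrow sampling for MRD/Flow, EDTA, PAXgene" at screening (Days −14 to −1) and then every 3 months. Section 3.3.4.2 says study MRD is measured mainly by flow cytometry.

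**Endpoint.** Section 6.3.2 has "Proportion of patients converting from MRD-positive to MRD-negative status at any time during treatment". Section 2.2.2 has "Proportion of patients converting from MRD-positive to MRD-negative status at any time", without the restriction to the treatment period, and the synopsis matches 2.2.2. None of the three names a reference sample.

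**Analysis.** Section 6.3 bases efficacy on "all patients who received at least one dose of any study drug". Section 6.3.2 applies the primary-endpoint method, which is a proportion with a two-sided 90% Clopper-Pearson interval. Section 6.3.1 counts patients lacking a post-baseline assessment as non-responders.

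**The concern.** Consolidation chemotherapy falls between the two candidate reference samples, so some patients may already be MRD-negative before their first idasanutlin dose. The plan does not say how they are scored.

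- **End of induction as reference.** Every dosed patient starts as positive. A patient cleared by consolidation who has a negative on-study sample becomes a converter, and the effect of earlier chemotherapy is credited to idasanutlin. The rate is biased up.
- **Screening as reference, all dosed in the denominator.** The same patient cannot convert but is still counted. The rate is biased down.

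Neither reading estimates conversion on idasanutlin among patients who could convert. The primary endpoint, CR at end of induction, does not apply to this cohort, and its EFS, OS and RFS clocks all start before study entry. MRD conversion is therefore its only response-type efficacy measure. There is no control arm to show the size of the bias, and the reference could be chosen after the data are seen.

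**Working it through.** **Inputs from the plan.** N = 30 (Section 6.1); denominator all dosed patients (6.3); two-sided 90% Clopper-Pearson interval (6.3.1, applied through 6.3.2).

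**Inputs assumed.** The documents give neither the share MRD-negative at entry (taken as 10%, 30% and 50%) nor the conversion rate among entry-positive patients (taken as 0% and about 20%, rounded to whole patients). All 30 are dosed, and each entry-negative patient has at least one negative on-study sample.

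**Method check.** For x of n, the lower limit is the 0.05 quantile of Beta(x, n − x + 1) and the upper limit is the 0.95 quantile of Beta(x + 1, n − x). For 14/20 this gives 49.2 to 86.0 (Table 14: 49, 86). For 17/20 it gives 65.6 to 95.8 (Table 15: 66, 96). The plan states no figure for MRD conversion itself.

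**Three codings.** Let m be the number negative at entry and c the number of true converters among the other 30 − m.
- A, end-of-induction reference: (c + m)/30
- B, screening reference, all dosed: c/30
- C, screening reference, screening-positive only: c/(30 − m)

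A − B = m/30, so each entry-negative patient moves the rate by 1/30 = 3.3 percentage points.

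**About 20% conversion among entry-positive patients** (90% CI in parentheses):

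| m | c | A | B | C |
|---|---|---|---|---|
| 3 (10%) | 5 of 27 | 8/30 = 26.7% (14.0, 43.0) | 5/30 = 16.7% (6.8, 31.9) | 5/27 = 18.5% (7.6, 35.1) |
| 9 (30%) | 4 of 21 | 13/30 = 43.3% (27.9, 59.8) | 4/30 = 13.3% (4.7, 28.0) | 4/21 = 19.0% (6.8, 38.4) |
| 15 (50%) | 3 of 15 | 18/30 = 60.0% (43.4, 75.0) | 3/30 = 10.0% (2.8, 23.9) | 3/15 = 20.0% (5.7, 44.0) |

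**No conversion at all (c = 0):**

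| m | A | B | C |
|---|---|---|---|
| 3 | 3/30 = 10.0% (2.8, 23.9) | 0/30 (0, 9.5) | 0/27 (0, 10.5) |
| 9 | 9/30 = 30.0% (16.6, 46.5) | 0/30 (0, 9.5) | 0/21 (0, 13.3) |
| 15 | 15/30 = 50.0% (33.9, 66.1) | 0/30 (0, 9.5) | 0/15 (0, 18.1) |

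With an inactive drug, coding A returns the entry-negative share. At m = 9, the A and B intervals from identical patients do not overlap.

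**Missing baseline.** The rule in 6.3.1 covers a missing post-baseline assessment only. Footnote n to Appendix 1, Table 4 ranks the EDTA sample ahead of MRD flow at screening, so a patient may have no flow baseline, and no rule covers that case.

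**The case against.** The best defence is that screening is the implied baseline. Section 6.3.2 speaks of converting during treatment, and a patient already negative at screening does not do so. Footnote a to Appendix 1, Table 4 ties baseline assessments to the screening window, and Section 4.5.8.1 uses the local end-of-induction result for enrolment. On that reading only the denominator is in question. The bias is then downward, and the numbers are closer: 4/30 = 13% against 4/21 = 19%, with widely overlapping intervals. The large contrasts all need the end-of-induction reading, and the entry-negative share is assumed.

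The consequences are also limited. This is one secondary endpoint with no hypothesis, target rate or precision claim, in a study that Section 6.8 describes as meant to generate hypotheses. Serial MRD results are collected and analysed under Section 6.3.3. Finally, a patient positive on a local molecular assay but flow-negative at screening may reflect assay discordance rather than clearance.

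Much of this stands as a limit on severity, and screening is a plausible baseline. It does not settle the matter. Section 2.2.2 and the synopsis omit the treatment-period restriction, and only the end-of-induction reference makes every dosed patient MRD-positive at the start, as an all-dosed conversion proportion presupposes. For this same cohort, 6.3.2 anchors EFS, OS and RFS before study entry, so a reader could carry that anchor over to conversion. Even on the screening reading, patients who cannot convert remain in the denominator. Assay discordance does not rescue the current text: a flow-negative patient cannot convert on flow, and would still be reported separately.

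**Conclusion.** The concern holds. The endpoint has no named reference sample, its stated denominator includes patients who may be unable to convert, and the same data support materially different rates. At an assumed 30% entry-negative share with about 20% true conversion, the rate is 43% or 13%, against 19% among patients at risk. At a 10% share it is 27% or 17%, against 19%. These figures illustrate an assumed range and do not predict the trial's bias, which depends on a share the documents do not give. The endpoint is descriptive and secondary, so this should be fixed but does not threaten the trial's primary conclusions. Confidence is medium.

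**What to change.** In Section 6.3.2:
- Define baseline as the scheduled screening MRD/Flow result.
- Restrict the conversion denominator to dosed patients who are MRD-positive on that sample.
- Count conversion during treatment on the same study flow assay, with the same negativity cut-off at screening and follow-up.
- Report patients MRD-negative at screening separately: how many, how many remained negative, how many became positive.
- State how a missing screening flow result is handled. For example, exclude these patients from the conversion denominator, report their number, and add a sensitivity analysis counting them as non-converters.

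Use the same wording in Section 2.2.2 and the synopsis. Confirmed and unconfirmed negativity may be shown descriptively.

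The change is to wording only: the sample is already scheduled, and no visit or aliquot order changes. The cost is precision, because the denominator falls below 30. In the 30% illustration, the 90% interval widens from about 23 points (28.0 − 4.7 = 23.3, for 4/30) to about 32 points (38.4 − 6.8 = 31.6, for 4/21). Some patients may also drop out of the denominator for lack of a flow baseline, since EDTA keeps first priority at screening.
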